## 7.2 General Methodology

### 7.2.1 General Summaries

All continuous variables will be summarized with means, medians, standard deviations, first and third quartiles, minimums, and maximums. For categorical variables the counts and percentages of subjects will be presented.

## 7.2.2 Kaplan-Meier Analyses

Survival analysis using the Kaplan-Meier (KM) method will be applied on time-to-event outcomes, for example safety related endpoints. The Kaplan-Meier estimate and the loglog transformed two-sided 95% confidence interval using the Greenwood standard errors will be reported at 1 month (30 days), 6 months (183 days), 1 year (365 days), 2 years (730 days), 3 years (1095 days), 4 years (1460 days), and 5 years (1825 days).

For subjects without an event, the date of censoring will be the latest date of all follow-up visits, assessments, and events (including death in those objectives where death is not the endpoint).

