16.7.2. Notification of Adverse Events

Sponsor Notification:

MDT18065EVR009 Version 5.006-Oct-2023

Page 66 of 121

Medtronic

Initial reporting may be done by phone, fax, e-mail, or on the eCRF completing as much information as is available. The original fully completed AE eCRF must be submitted to Medtronic as soon as possible.

As soon as possible (desired within 24 hours of investigator or study coordinator awareness), the investigational center staff must report all SAE, and SADE to Medtronic. For the previously mentioned events, the AE eCRF will be completed with all known details as soon as possible, this will serve as notification to Medtronic. If the study database cannot be accessed due to technical problems, contact the sponsor via email, phone, fax and provide the known details of the event. Once the access issue has been corrected, the event should be entered onto an AE eCRF.

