16.7.3. Expedited Safety Reporting Requirements

Documentation of GCP office and EC notification of any safety event must be kept at the investigational center and a copy sent to the sponsor.

It is the responsibility of the investigator to follow their EC reporting requirements.

Timeframes and mechanisms for the clinical site reporting adverse events to EC, and Medtronic will still refer to NMPA GCP for Medical Devices²³ (China GCP 2022) listed in Table 5.

Version 5.006-Oct-2023

Page 67 of 121

Table 5. Investigator Reporting Requirements for AE and Device Deficiencies

For the following events, reporting requirements are:						
Serious Adverse Events (SAE)						
Investigators shall report to (China GCP 2022 Article 32):						
Medtronic	Within 24 hours					
GCP office	Within 24 hours					
EC	Within 24 hours					
For the following events, reporting requirements are:						
Investigators shall record adverse events and device deficiencies identified during clinical trials of medical devices. (China GCP 2022 Article 31)						
To Medtronic	Submit AE and DD in a timely manner after the investigator first learns of the event.					
To EC and GCP office	Submit event analysis report per EC's requirements					

NOTE: In case there is/are additional AE reporting requirement(s) and/or process(es) (e.g. internal hospital policy or province regulatory authority instruction, etc.), these specific AE reporting requirement and process must be documented in a separate cover.

Timeframes and mechanisms for the sponsor submitting adverse events to local regulatory authorities and other clinical Research institutions and investigators participating in the study per the NMPA GCP for Medical Devices²³ (China GCP 2022) are listed in Table 6.

[figure not shown]
Table 6. Sponsor Reporting Requirements for AE and Other Serious Safety Issues

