#### **Introduction** 3.

This Statistical Analysis Plan has been designed to document, before data are analyzed, the rationale for the study design, and the planned analyses that will be included in study reports. This statistical analysis plan is developed based on the Clinical Investigational Plan (CIP) Revision 5.0. As of CIP 5.0, the study transitioned to the post-market phase.

The purpose of this study is to evaluate the safety and efficacy of the Medtronic CoreValve™ Evolut™ PRO System when used by Chinese implanting centers in patients with severe symptomatic aortic stenosis (AS) who are at high risk for Surgical Aortic Valve Replacement (SAVR). The study population will include males and females with severe symptomatic aortic stenosis who are considered at high risk for SAVR. This is a prospective, observational, single arm, interventional, multi-center, post-market study.

Revision 3.0

Page 6 of 23

Data will be analyzed and Clinical Study Reports (CSRs) will be prepared for the primary endpoint (at 30 days) and annually through 5 years. The final analysis will be performed when all implanted subjects have completed their 5-year follow-up.

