#### 2. All-cause mortality at 6 months, one year, and annually through 5 years

Event rate estimates will be provided at 6 months, 1 year and annually through 5 years for the attempted implant set. The outcome is descriptive including Kaplan-Meier rates and no statistical hypothesis test is specified.

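### Annual reports could overstate Kaplan-Meier mortality at time points that not every subject has reached, because survivors are censored at their last recorded contact while deaths can be known sooner

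*SAP*

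**What the plan says.** **Censoring.** SAP 7.2.2: "For subjects without an event, the date of censoring will be the latest date of all follow-up visits, assessments, and events". No data cut-off date is named as a censoring date. SAP 7.4 adds that drop-outs are censored at discontinuation; it does not address subjects still in follow-up.

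**Estimates.** SAP 7.2.2 specifies "The Kaplan-Meier estimate and the loglog transformed two-sided 95% confidence interval using the Greenwood standard errors will be reported" at seven time points, from 30 days to 5 years (1825 days). For mortality, SAP 7.10.5 item 2 says: "Event rate estimates will be provided at 6 months, 1 year and annually through 5 years for the attempted implant set". Neither section limits a report to time points that all subjects have reached.

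**Reports.** SAP section 3 says that clinical study reports "will be prepared for the primary endpoint (at 30 days) and annually through 5 years". Protocol 10.1 leaves the annual reports to the sponsor's discretion.

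**Contact with subjects.** Protocol Table 3 and SAP 5.3 schedule one visit a year after year 1, in the 30 days after the implant anniversary.

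**Reporting of deaths.** Death is a serious adverse event (Protocol 16.2). Protocol 16.7.2 asks for prompt reporting: "desired within 24 hours of investigator or study coordinator awareness), the investigational center staff must report all SAE, and SADE to Medtronic". Protocol Table 5 gives "Within 24 hours" for reports to the sponsor, the GCP office and the ethics committee.

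**The concern.** Kaplan-Meier estimation needs censoring to be unrelated to outcome. Here the time since a subject's last visit is treated differently according to outcome. A subject who dies in that interval and whose death is reported contributes an event and the time up to it. A subject who lives through the same interval, with no other recorded contact, is removed at the last visit. The risk set is too small for the events counted in it, and the estimate moves upward.

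At a year-k snapshot, this affects subjects between their year-k and year-(k+1) visits. Entry was staggered over about 1.5 years, so there will be many of them. A year-(k+1) figure shown at that point would tend to be too high and then fall in the next report as survivors complete their visit. The log-log Greenwood interval does not allow for this, because it also assumes non-informative censoring.

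The study is descriptive, with no hypothesis or pass/fail criterion, so the point estimates are its product. Protocol section 22 says that reports after the primary endpoint report may support new device generations.

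**Working it through.** The documents give no expected mortality and no figure for this bias, so there is nothing of the plan's own to reproduce. The size has to be worked out from stated assumptions.

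**Inputs from the documents**
- Entry period: 6.5-year study minus 5-year follow-up = 1.5 years, or 547.5 days (Protocol 9.1.5.5).
- Visit windows: days 30–45, 183–210 and 365–395, then each anniversary plus 30 days (SAP 5.3).
- Primary population: 50 attempted implants (SAP 6).

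**Assumptions**
- Entry is uniform and the hazard constant, with yearly mortality of 5%, 10% or 15%.
- There are no losses or missed visits.
- The snapshot falls 45 days after the last-entered subject's year-k anniversary.
- In the base case every death is known at once and there is no contact between visits.

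**Hand calculation: year-1 report, 2-year figure, 10% yearly mortality**
1. Follow-up at the snapshot runs from 365 + 45 = 410 days to 410 + 547.5 = 957.5 days. The share that has reached day 730 is (957.5 − 730)/547.5 = 41.6%.
2. Take 100 subjects alive at year 1. The 41.6 who have reached year 2 yield 41.6 × 0.10 = 4.16 deaths in the second year.
3. The other 58.4 have follow-up of 410 to 730 days, mean 570, so on average 570 − 365 = 205 days (0.56 year) beyond year 1. Deaths: 58.4 × (1 − 0.9^0.56) ≈ 3.4.
4. Under the SAP rule the 58.4 − 3.4 = 55.0 survivors of that group leave at about year 1, so about 45.0 remain at risk. The second-year risk is estimated as (4.16 + 3.4)/45.0 ≈ 16.8%, against a true 10%.
5. Two-year mortality: 1 − 0.90 × (1 − 0.168) ≈ 25%. Truth: 1 − 0.90² = 19.0%.

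**Simulation of the same set-up** (200,000 subjects, visits spread over their windows). Each cell gives the SAP-rule estimate against the truth for year k+1 in a year-k report:

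| Yearly mortality | k=1 | k=2 | k=3 | k=4 |
|---|---|---|---|---|
| 5% | 13.4 vs 9.8 | 17.8 vs 14.3 | 21.9 vs 18.6 | 25.5 vs 22.6 |
| 10% | 25.3 vs 19.0 | 32.9 vs 27.1 | 39.5 vs 34.4 | 45.5 vs 41.0 |
| 15% | 36.1 vs 27.8 | 45.4 vs 38.6 | 53.8 vs 47.8 | 60.5 vs 55.6 |

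The bias runs from about +3 to about +8 points. At year k itself, and at year 5 in the final analysis, the SAP-rule estimate equals the one with everyone followed to the snapshot. In 4,000 simulated trials of 50 subjects at each mortality level (k=1), the SAP-rule estimate was never below the full-follow-up estimate. Their mean was 13.6%, 25.2% and 35.9%.

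**Relaxing the base case.** With hazard 0.10 per year the true 2-year figure is 1 − exp(−0.2) = 18.1%. In a year-1 report:
- all deaths known at once, no extra contacts: about 24% (+6);
- half of deaths learned before the next visit, no extra contacts: about 21% (+3);
- half learned early, one extra dated contact per subject-year: 19.4% (+1.3);
- half learned early, two extra contacts: 18.6% (+0.5).

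With 10% yearly mortality (truth 19.0%) and no extra contacts, 25% of deaths learned early gives 20.7%. If none is learned early there is no bias.

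**The case against.** **The 24 hours.** A reader might infer that every death is in the database a day after it happens. The documents do not say so: Protocol 16.7.2 starts the clock at site awareness and calls 24 hours desired. With one scheduled contact a year, a death away from the study hospital may be learned only at the next contact. This stands, and it makes the base case close to an upper bound.

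**The censoring date.** It is also tempting to read the rule as censoring at the last visit. It takes assessments and events too, and Protocol 9.2.5 provides for unscheduled visits and telephone calls. A survivor's later adverse event, or a dated contact recorded as a visit or assessment, moves the date forward. This also stands. It reduces the bias without removing it: one extra contact per subject-year, with all deaths known early, lowers 25.3% to 22.9% (truth 19.0%).

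**Which figures a report shows.** A reader might infer that the SAP requires all seven time points in every annual report. It does not. It lists them for the study, SAP 7.9 places analysis after data collection and cleaning, and the protocol makes annual reports optional. A year-k report that stops at year k is unbiased in these calculations. But the SAP says that annual reports will be prepared, and nothing in it stops a year-k report from showing year k+1.

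**Importance.** These are other outcome measures with no decision criterion, and with 50 subjects the estimate is visibly imprecise. In the base case with hazard 0.10, the average 95% interval runs from about 12% to 45%. Its coverage is still only about 84 to 85%, so imprecision does not fully hide the bias.

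**Conclusion.** The point holds in conditional form. The SAP's censoring rule makes Kaplan-Meier mortality likely to be overstated at any time point that only part of the cohort has reached, if an annual report shows such a point and some deaths are learned before the next visit.

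The size is about +3 to +8 points under assumed yearly mortality of 5 to 15%, immediate knowledge of all deaths and no contact between visits. It is about +1 to +3 points if half of deaths are learned early, depending on survivor contacts, and can vanish if few are. Mortality, the share of deaths learned early, contact frequency and snapshot timing are all assumptions; the documents give none of them.

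Stroke, myocardial infarction and life-threatening bleeding share the mechanism, but their bias was not quantified.

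A reader might go further and infer that the primary result or the final 5-year mortality is biased. The documents do not support that. The 30-day analysis followed the primary population's 30-day follow-up, and the final analysis waits until all implanted subjects have completed 5 years. This is a cheap improvement to the annual reports and does not undermine the main results.

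**What to change.** Add to SAP 7.2.2: *In any report before the final analysis, Kaplan-Meier estimates are given only up to the latest time point listed in this section for which the visit window of every subject has closed. Follow-up is truncated at that day: later events do not enter the estimate, and event-free subjects are censored no later than that day. Later events are still shown in the safety listings.*

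The cost is this SAP text and a truncation line in the program. It needs no extra visits and leaves the completed 30-day analysis unchanged. The downside is that an annual report gives no early Kaplan-Meier figure for a year that only part of the cohort has reached. Keeping later events in the listings means that no observed death goes unreported.

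Confirming vital status for everyone at the snapshot and censoring there would also correct mortality. It needs site contacts outside the visit schedule and would not by itself correct the non-fatal outcomes, so it should not be relied on.

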#### 7.10.5 **Other Outcome Measures**

#### 1. Event rates of the following TAVI-related complications:

Revision 3.0

Page 21 of 23

- change to surgery
- o need for cardiopulmonary mechanical assistance
- coronary occlusion or obstruction
- annular rupture or dissection
- ventricular perforation
- mitral valve damage
- prosthetic valve displacement, migration, or embolism
- acute kidney injury (up to 7 days post procedure)

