#### Data Collection and Analysis Method:

Event rate estimates for each of the above TAVI-related complications will be provided at 30 Days, 6 months, 1 year and annually through 5 years for the attempted implant set. The outcome is descriptive including Kaplan-Meier rates and no statistical hypothesis test is specified.

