#### All stroke (disabling and non-disabling) at 6 months, one year, and annually through 5 years

Event rate estimates will be provided at 6 months, 1 year and annually through 5 years for the attempted implant set. The outcome is descriptive including Kaplan-Meier rates and no statistical hypothesis test is specified.

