#### 7. Prosthetic valve endocarditis at 30 days, 6 months, one year, and annually through 5 years

Event rate estimates will be provided at 30 days, 6 months, 1 year and annually through 5 years for the attempted implant set. The outcome is descriptive including Kaplan-Meier rates and no statistical hypothesis test is specified.

Revision 3.0

Page 22 of 23

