#### 8. Prosthetic valve thrombosis at 30 days, 6 months, one year, and annually through 5 years

Event rate estimates will be provided at 30 days, 6 months, 1 year and annually through 5 years for the attempted implant set. The outcome is descriptive including Kaplan-Meier rates and no statistical hypothesis test is specified.

9. Valve-related dysfunction, defined as moderate or severe prosthetic valve stenosis, or moderate or severe prosthetic regurgitation (per VARC II) at one year and annually through 5 years

Event rate estimates will be provided at 1 year and annually through 5 years for the implanted set. The outcome is descriptive including proportion rates and no statistical hypothesis test is specified.

10. Valve-related dysfunction requiring repeat procedure at 30 days, 6 months, one year, and annually through 5 years

Event rate estimates will be provided at 30 days, 6 months, 1 year and annually through 5 years for the attempted implant set. The outcome is descriptive including Kaplan-Meier rates and no statistical hypothesis test is specified.

- 11. Valve hemodynamic performance metrics by Doppler echocardiography at one year and annually through 5 year
  - a. Mean aortic gradient
  - b. Effective orifice area
  - c. Degree of aortic regurgitation (transvalvular, paravalvular, total)

The echocardiographic measurements will be reported at 1 year and annually through 5 years for the implanted set with site-reported echocardiographic data. No statistical hypothesis test is specified.

For mean gradient and effective orifice area, the descriptive statistics (mean, median, standard deviation, minimum, maximum and interquartile ranges) will be presented.

Degree of aortic regurgitation will be reported as proportions.

12. New York Heart Association (NYHA) functional classification at 30 day, 6 months, one year and annually through 5 years

[figure not shown]
NYHA classifications will be summarized with frequencies and percentages at 6 months, one year and annually through 5 years. All attempted implant subjects with available NYHA collections (I/II/III/IV) will be included in the analysis. No statistical hypothesis test is specified.

13. Post-operative EQ-5D quality of life at 30 days and one year

EQ-5D will be summarized with means, medians, standard deviations, minimums, maximums, and interquartile ranges, at 30 days and 1 year for the attempted implant set. No statistical hypothesis test is specified.

Revision 3.0

Page 23 of 23

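### Late non-fatal outcomes are reported as Kaplan-Meier rates with deaths censored, so where deaths precede later events the rate exceeds the share of patients affected; no competing-risk estimate is planned

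*SAP*

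**What the plan says.** SAP 7.2.2 applies Kaplan-Meier to time-to-event outcomes, with log-log intervals from Greenwood standard errors, at 30 days, 6 months and each year to year 5. A subject without the event is censored at the latest date among visits, assessments and "events (including death in those objectives where death is not the endpoint".

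SAP 7.10.5 applies this to the late outcomes:

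- Item 1, TAVI-related complications: "Event rate estimates for each of the above TAVI-related complications will be provided at 30 Days" and then to 5 years. The list includes "prosthetic valve displacement, migration, or embolism".
- Item 3, stroke: "Event rate estimates will be provided at 6 months, 1 year and annually through 5 years for the attempted implant set".
- Items 4, 5, 7, 8 and 10 (myocardial infarction, life-threatening bleeding, endocarditis, valve thrombosis, repeat procedure): "Event rate estimates will be provided at 30 days, 6 months, 1 year and annually through 5 years for the attempted implant set".
- Each of these carries the sentence "The outcome is descriptive including Kaplan-Meier rates and no statistical hypothesis test is specified".

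Item 2 is all-cause mortality, where death is the event. Item 9, valve-related dysfunction, is a simple proportion: "Event rate estimates will be provided at 1 year and annually through 5 years for the implanted set". SAP 7.2.1 adds a general rule: "For categorical variables the counts and percentages of subjects will be presented".

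Neither document mentions competing risks or cumulative incidence. The sensitivity analyses in SAP 7.10.1 and 7.10.2 concern only the 30-day primary endpoints.

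**The concern.** A patient who has died cannot later have endocarditis or a repeat procedure. Censoring at death treats that patient as if still at the same risk as those alive. The resulting 1-KM estimates the risk in a setting where nobody dies, and only if death is independent of the event. It is not the proportion of patients who had the event.

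The SAP calls the output an event rate, so a reader may well take it as that proportion. Subjects are 65 or older and at high surgical risk (Protocol 9.1.5.1 and 9.1.5.2), so deaths over 5 years are foreseeable, and the SAP itself plans mortality at every annual time point. Protocol section 6 says the data may support registration of new device generations or expanded indications. In a descriptive study the estimate is the result, so what it measures should be clear.

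**Working it through.** The plan states no late event rate or late mortality, so there is no figure of its own to reproduce.

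**Inputs.** From the documents: n = 50 attempted implants (SAP 6), death censored (SAP 7.2.2), time points to 5 years (SAP 7.10.5). Assumed: 5-year competing mortality m of 20-60%, 5-year 1-KM (F) of 5-20%, no other censoring.

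**1. Constructed cohort.** Take 50 patients, 20 deaths spread over 5 years, 4 patients with the event, no loss to follow-up. The true proportion affected is 4/50 = 8.0%, and Aalen-Johansen returns 8.0% in every arrangement. The 1-KM figure is:

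- 8.0% if all 4 events precede the first death;
- 10.4% if the events are spread over years 1 to 5;
- 11.7% if they fall in years 3 to 5.

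The excess therefore depends on deaths coming before later events.

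**2. Constant hazards.** Event hazard a = -ln(1-F)/5; death hazard b = -ln(1-m)/5; cumulative incidence CIF = a/(a+b) × (1 - exp(-5(a+b))).

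Example, F = 10% and m = 40%: a = 0.02107, b = 0.10217, a+b = 0.12324. CIF = 0.1710 × (1 - 0.5400) = 7.87%. Ratio = 10/7.87 = 1.27.

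| 5-year 1-KM | CIF, m = 20% | CIF, m = 40% | CIF, m = 60% | Ratio |
|---|---|---|---|---|
| 5% | 4.49% | 3.92% | 3.29% | 1.11-1.52 |
| 10% | 8.98% | 7.87% | 6.60% | 1.11-1.52 |
| 20% | 18.0% | 15.8% | 13.3% | 1.11-1.50 |

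Over the same ranges the ratio is below 1.01 at 30 days, 1.02-1.09 at 1 year and 1.07-1.30 at 3 years. With m = 10% it is 1.05 at 5 years.

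**3. Against sampling error.** Greenwood SE = (1-F) × sqrt[ a/(50(a+b)) × (exp(5(a+b)) - 1) ]. In the example, SE = 0.9 × sqrt(0.1710/50 × 0.8519) = 4.9 points; the gap is 2.13 points, or 0.44 SE. Across the table the gap is 0.16 to 0.92 SE, or 0.3 to 3.3 patients of 50.

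**4. Timing of events.**

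- Early: with half of the observed events by day 30, the 5-year ratio is 1.06-1.27.
- Late: with no events before year s and a constant hazard after, a = -ln(1-F)/(5-s) and CIF = exp(-bs) × a/(a+b) × (1 - exp(-(a+b)(5-s))). For s = 2 or 3 the ratio runs from 1.17 to 2.07. At F = 20% and m = 60% the gap is 1.17 SE (s = 2) or 1.25 SE (s = 3). For s = 3: CIF = 0.5771 × 0.3784 × 0.4455 = 9.7%, against 20%.

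**5. Deaths that are the event.** Protocol Appendix V counts some deaths as stroke, spontaneous myocardial infarction or life-threatening bleeding. If 10% of deaths are the event itself (assumed), b becomes 0.9b. At F = 10% the ratio is then 1.10-1.46.

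**6. Protocol 10.4.** Attrition and loss to follow-up are expected below 20% over 5 years; the text does not say whether deaths count. If they do, m is at most 20%. The ratio is then at most about 1.11 under constant hazards and about 1.2 with late events.

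**The case against.** The best case for leaving the plan alone is that the censoring rule is stated openly, so the quantity is defined; the outcomes are descriptive; no pass/fail criterion exists; and all-cause mortality is reported at the same late time points, so a reader can see how much death there was. This stands as a reason for low severity. It does not remove the point: the mortality curve shows that deaths occurred but does not give the proportion with the event, and the confidence interval is centred on the net risk.

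Counts might be shown anyway. The general rule in SAP 7.2.1 and the word *including* in 7.10.5 do not exclude them, but nothing commits to events and competing deaths for these outcomes.

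The size rests on assumptions. That also stands. The upper ratios need high mortality or late events, and one reading of Protocol 10.4 would rule out most of the mortality range.

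A reader might infer that every Kaplan-Meier outcome in SAP 7.10.5 is inflated. The documents do not support that. All-cause mortality is not affected, because death is the event. Where events come before deaths the two estimates agree, so change to surgery, cardiopulmonary support and acute kidney injury to 7 days are essentially untouched. A reader might equally infer that the gap always lies within one standard error; late events at high mortality break that.

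**Conclusion.** The point holds, at low severity. For SAP 7.10.5 items 3, 4, 5, 7, 8 and 10, and for item 1 components that can occur after the procedure, the planned rate is a net risk. It overstates the proportion affected whenever deaths precede later events, and no competing-risk estimate is specified.

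Under the assumed rates and constant hazards, the 5-year overstatement is 11% to 52% in relative terms and under one standard error. It is less with early events and more with late ones. These figures show a range; they are not predictions for this trial.

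It would go too far to call Kaplan-Meier an error here or to doubt the main results. Kaplan-Meier is a valid estimate of net risk if death is independent of the event. The 30-day endpoints, all-cause mortality, the VARC II composite (which counts death as an event) and item 9 are essentially unaffected.

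**What to change.** Add to SAP 7.2.2:

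> For 7.10.5 items 3, 4, 5, 7, 8 and 10, and for item 1 coronary occlusion or obstruction, mitral valve damage, and prosthetic valve displacement, migration or embolism, the Aalen-Johansen cumulative incidence with 95% CI will be reported at 1, 2, 3, 4 and 5 years beside the Kaplan-Meier estimate. Deaths that are not themselves the adjudicated event are the competing event.

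Label the Kaplan-Meier estimate *deaths censored (net risk)*, and show the number of events and of competing deaths at each time point. Leave all other analyses unchanged.

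The three item 1 components are named because Protocol Appendix V, section 2.0, lets them occur after the procedure. Annular rupture or dissection is left out: Appendix V mentions these only within major vascular complication, without a time limit, and a missing limit is no evidence of late events. Ventricular perforation is also left out. Section 2.0 allows a late septal perforation, but the SAP item does not say which form it means; it can be added on the same terms if late events are thought plausible.

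**Cost.** One paragraph, one output column and two counts per time point: 9 outcomes × 5 time points = 45 extra estimates and 90 counts. Deaths are already collected and adjudicated. Kaplan-Meier stays, which fits the Protocol 10.8 principle of not changing major methods. The downside is two estimates per late outcome, many resting on few events at n = 50, so the labels must be clear. If that is too much, the label and the counts alone would prevent most of the misreading.
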